9.1. Timing of Assessments

See Section 17

9.2. Clinical Assessments and Interventions

9.2.1. Patient Characteristics and Medical History

Demographic information (age, gender, race) will be captured at Screening. Relevant medical history, prescription drugs, including history of smoking, other pertinent history and information regarding underlying diseases will be recorded at Screening.

9.2.2. Vital Signs

Heart rate, respiration rate, and oxygen saturation measurements will be performed and recorded after resting for 5 minutes during the training call and at the week 13 final phone visit.

9.2.3. Spirometry

Patients will be performing slow spirometry measurements five (5) times per week on Sundays, Mondays, Wednesdays, Fridays and Saturdays. They will be performing forced spirometry measurements on Tuesdays and Thursdays. Measurements will be performed in the morning at least 15 minutes following them taking their inhaled medications. The reliability and repeatability of effort dependent tests or tests that require patients to follow specific steps, depend on patients understanding how to perform the test.

The GoHome comes with Avatar-Assisted-Technology to coach the patient through each measurement. The Avatar follows ATS/ERS recommendations for instructions and coaching. At the end of each measurement, the Avatar reviews the results and instructs the patient how to correct maneuver errors. All of this takes place without human intervention. Experience to date indicates that use of the Avatar-Assisted-Technology results in data collection as good as from hospital PFT laboratories and better than from physician offices.³

Spirometry will be performed in accordance with the 2019 ATS/ERS recommendations for intra-measurement performance. To increase adherence to performing spirometry measurements, a Statistical Process Control approach will be used as recommended for COPD patients.⁴ This approach will be used for both FVC and SVC testing.

9.2.4. Oxygen Saturation

Oxygen saturation will be measured by pulse oximetry at all clinic visits and daily while the patient is monitored at home. Oxygen saturation will be measured prior to the measurement of spirometry.

9.2.5. Quality of Life (QoL) Surveys

The COPD Assessment Tool (CAT), a validated survey, consisting of 8 questions, each on 0-5 Likert scale, will be used to assess the patient's health and quality of life. Patients will be asked to fill it out at enrollment and again at the end of weeks of 4, 8 and 12.

9.2.6. Medication Adherence

Automatic reminders will be sent to patients on their GoHome to take medications. Patients will self-report in response to the reminders whether or not they took their medications. The medication tracking function of the MTI CarePortal will provide report cards to patients (and optionally copied to healthcare providers) as to their adherence, on each Monday for the previous week. These reminders can also be issued "on demand" by the healthcare providers monitoring the patients directly from the MTI CarePortal.

9.2.7. Measurement Adherence

Automatic reminders will be sent to patients on their GoHome to perform measurements. The measurement tracking function of the CarePortal will generate alerts to healthcare providers as to their adherence, based on programmed alarm settings.

9.2.8. Incidence of Clinical Interventions

Clinic personnel will maintain records of any changes in clinical care, additional clinic visits or hospitalizations during the monitoring period. These will be used to determine the effectiveness of the monitoring in either identifying the need for a clinical intervention or preventing the need for one.

9.2.9. COPD Action Plan

The MTI CarePortal architecture includes the MTI CareBook that provides the ability to implement a specific patient-centric COPD Action Plan with appropriate cultural and literacy considerations. The CareBook enables the Action Plan through the use of two primary functions, CareText® and CareTips.

CareText® generate engagement with patients using its ability for simple bi-directional messaging using questions with pre-formatted responses, requiring only a single key response to answer the question. These CareTexts can be sent in several different formats including Yes/No, emoticons, multiple choice, or a slide bar scale. The questions as well as the responses are stored and are viewable on the MTI CarePortal. CareTexts can be automatically sent out as part of a CareBook, maintaining engagement and collecting simple feedback from patients.

CareTips are a shorthand approach to educate the patients about their disease, how to improve their quality of life, and to have them execute small concepts that the caregivers want them to do. These can be something as simple as a health tip to a streaming video on any subject matter.

An interactive COPD Action Plan, built around the MTI CareBook will be used to engage patients during the study. The contents of the Action Plan are in the Appendices.

9.2.10. Usability Questionnaire

At the End-of-Study phone call, the patient will be given a brief Usability Questionnaire to collect their opinions on use of the GoSpiro and GoHome, both for usability and perceived value to them and the management of their health. The Usability Questionnaire is in the Appendices.

10. Data Collection and Confidentiality Procedures

The data collection tablets placed in patients' homes are based on the Android operating system. They are locked down with a Samsung Knox Mobile Device Management (MDM) control system that prevents anyone from making changes to the programs or applications. Although the tablets connect with the MTI CarePortal via the internet (either Wi-Fi or cellular), patients have no access to the internet outside of the applications running on the tablet.

For each patient, a randomized numeric token is sent to the data collection device in their home. All data collected from proprietary data collection devices such as the GoHome Personal Health Monitor or the GoClinic Android tablet are then returned to the server with the token. When received, the server reidentifies the data based on the token number and locates the data in the appropriate patient file. No personal health information (PHI) is ever transferred between a remote location and the MTI CarePortal. The access to the data storage system on the MTI CarePortal is limited to web browsers (SSL Secured), direct messaging and electronic data transfer facilitated with a data token.

The MTI CarePortal cloud server, where the data is stored, is hosted by Expedient Inc. with the main server located in, Dublin, OH. Operating mirrored drives, data is backed up in Pittsburgh, PA. The system contains a disaster recovery center in Carmel, IN. Expedient is a global data management company that complies with HIPAA, HITRUST and GDPR requirements for data security.

Settable authorization levels limit users to a) inquiry (read only) capabilities, b) inquiry with also the ability to set alarm limits, establish reminders, care plans and the like, and c) full access for editing and updating capabilities depending on the level of authorization. Users have no access to the underlying code running the user facing application or the MTI CarePortal infrastructure.

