7.4. Study Procedure

Patients will be enrolled in the study for up to fifteen (15) weeks, including twelve (12) weeks for active monitoring. The study timeline for all procedures is defined in the Section 17 table. All patients enrolled in the study, following the collection of a verbal informed consent, will have a medical history recorded by phone. Upon confirmation of basic eligibility, patients will be sent a telemonitoring system consisting of the GoSpiro®, a pulse oximeter and a GoHome tablet. A member of the Clinic research staff will schedule a (virtual (phone or video) appointment with the patient for when the system has arrived. They will train each patient on how to use the devices and will instruct the patient how and when to record measurements. Pulse oximetry (SpO2 and HR), as well as slow and forced spirometry with the GoSpiro will be collected during this training call. These instructions will also be provided on patient information material (See Appendices A and B). Patients should exhibit proficiency with the devices and demonstrate understanding of the measurement schedule prior to ending the call.

The study nurse will contact the patient the following day by phone to confirm that the patient is able to set up the GoHome and use the devices for measurements. In the event the participant is not able to provide and transmit satisfactory data collection after one week (due to technical or training reasons) they will be removed from study and replaced with another participant toward the total recruitment goal. The study nurse will call the patient every four (4) weeks to collect information on any changes to inhaled medication, steroids or antibiotics and assist the patient with any operational questions. Between phone calls, Clinic research staff or device manufacturer's support personnel will be available to assist the patient should questions or technical issues arise. The study nurse will conduct a final phone visit to collect close out data prior to the participant returning the devices (see Section 17).

Physiologic data from the patients will be transmitted automatically following each measurement and will be available on the CarePortal within a few minutes of its collection. Physiologic data (spirometry and oxygen saturation) will be collected every day. Medication reminders, COPD Action Plan communications, etc. will be sent every day if scheduled. In addition to monitoring parameters, health

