teaching tips as part of the COPD Action Plan will also be incorporated into the GoHome software to educate and motivate patients regarding self-care. A Quality of Life questionnaire (COPD Assessment Test) will also be collected every 4 weeks from the patients through the GoHome tablet.

At the end of study (after completion of final phone visit), the patients will return the equipment to UNC via a pre-paid FedEx air bill that has been included with the original shipment. A member of the Clinic research study team will have a final call with the patient to check on the patient's respiratory status and have them complete a usability questionnaire by phone.

8. Quality Control Measures

Quality control of the lung function measurements will include automatic ATS/ERS intra-measurement grading of the forced flow-volume loops and slow spirometry to ensure interpretable and actionable home spirometry.⁵ MTI will assist with determining the number of missed spirometry sessions with seven times per week testing, and determining any technical issues in transmission of data from the spirometer to the MTI CarePortal.

The GoSpiro home spirometer meets the 2019 ATS/ERS criteria for accuracy and reproducibility.⁵ Baseline pulmonary function will be defined as the mean FEV1 over the first two weeks of the study (six measurements). If older data is available for the patient, that data may be included in establishing historic values for analysis. Variability of pulmonary function for alerts to Clinic staff will include a decrease by one personalized z-score using pulmonary function measurements for an individual patient and calculated over the length of the study as well as using historic data if available.

Alerts from acute declines in pulmonary function will be defined as any decrement in either FEV1, FVC or IC >10%. Oxygen saturation readings below 88% will trigger an alert. For patients being managed with DPI delivered inhaled drugs, monitoring of peak inspiratory flow for detection of inadequate flows to aerosolize and deliver the powder, will also generate alerts. The MTI CarePortal will provide daily reports to the Clinic research staff of patient trending towards alert levels, as well as patients with low adherence to medications or measurements.

9. Assessments

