Differences between important continuous variables at two specific times will be evaluated with the two-sided paired t-test ($P<0.05$). Important categorical events such as changes in FEV1, Inspiratory Capacity, QoL, medication adherence, rehospitalization and incidence of adverse events will be evaluated by constructing 95% confidence limits in their incidence, and also with descriptive statistics. In addition, the results will be used to identify technological deficiencies and provide data to inform the power requirements for future studies.

Primary Endpoint Definitions

The first primary endpoint variable for this study is the change from baseline in Total Score of COPD Assessment Test (CAT). The total CAT score is calculated by summing the scores of all items and ranges from 0 to 40, higher scores indicating severe condition. The change will be calculated as the CAT score at Week 12 minus the CAT score at Enrollment. A negative change in CAT score will indicate an improvement in patient status.

The second primary endpoint variable for this study is adherence to performing scheduled measurements and responding to scheduled questionnaires. For each subject the adherence will be recorded based on the data uploaded to the CarePortal. The adherence percentage will be calculated by the difference in recorded measurements and answered questionnaires versus the scheduled measurements and questionnaires.

Analysis of Primary Endpoints

The primary outcomes will be reported as proportions with 95% confidence intervals, on the FAS.

Secondary Endpoint Definitions

The prespecified secondary endpoints for this study will include:

- Participant satisfaction survey scores at 3 months (Time frame: 3 months) defined as the percentage of participants with score of 4 or higher on individual survey domains. A satisfaction survey (investigator-developed, 15 questions, each question is graded on a scale of 1-5, 1 being not at all and 5 being extremely) will be used to measure home spirometry and table ease and usefulness.
- Rate of self-reported COPD exacerbations (Time frame: 3 months) defined as the 30-day COPD exacerbation rate, defined as the mean number of events/30 days of follow-up (using three months of follow-up data). COPD exacerbation events are defined as self-reported COPD exacerbations requiring treatment with antibiotics or steroids.

Analysis of Secondary Endpoints

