The secondary endpoints will be reported as proportion with 95% confidence interval of participants with score of 4 or higher on individual survey domains of patient satisfaction summary score; Descriptive analysis of patient satisfaction summary scores will include mean (SD), median (IQR), range of scores.

For the COPD exacerbation analyses, the proportion of patients with COPD exacerbations and the rate of exacerbations occurring during follow-up will be reported along with 95% CI. A patient will be considered censored for exacerbations at the time of the last documented visit, the end of the study, or death (whichever occurs earlier), if they did not experience an exacerbation before.

Exploratory Endpoints Definitions

The study contains exploratory endpoints to examine individual components of the monitoring functions and their impact. These include:

- Rate of self-reported COPD exacerbations stratified by FEV1 and defined as the 30-day COPD exacerbation rate, defined as the mean number of self-reported COPD exacerbations

requiring treatment with antibiotics or steroids per 30 days of follow-up (averaged using 3 months of follow-up data), stratified by FEV1 (separately <50% predicted and >=50% predicted).

- Home spirometry measurement collection adherence defined as the percentage of participants achieving >50% completion of spirometry measurements over three months.
- Home pulse oximetry measurement collection adherence defined as the percentage of participants achieving >50% completion of pulse oximetry over three months.
- Home questionnaire collection adherence defined as the percentage of participants achieving >50% completion of home questionnaires over three months.
- Quality of home forced spirometry measures defined as the percentage of forced home spirometry measurements that meet ATS quality standards
- Change from baseline on COPD Assessment Test (CAT) Total Score defined as the CAT scores measured at baseline, week 4, week 8 and week 12 and the median (SD) change in CAT score from baseline will be calculated at each time point.
- Inspiratory Capacity variability defined as the coefficient of variation will be calculated by dividing standard deviation of Inspiratory Capacity values by the mean of the inspiratory capacity values. Inspiratory capacity measured via slow vital capacity maneuver will be performed at home five days per week during duration of study.

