15.4. ClinicalTrials.Gov Registration

As this study meets the FDAAA 801 definition of an “Applicable Clinical Trial”, it is required that the study be registered on ClinicalTrials.gov. The Principal Investigator will register and activate the study account prior to enrollment, and all results will be entered upon study completion, following statistical analysis, per the Results Database Guidelines.

16. References

1. US Government, Hospital Readmissions Reduction Program, Section 3025 Affordable Care Act. 2012.
2. Sheshadri A., et al. In submission. Personal communications. 2019
3. Stenzler A. Collecting Quality Spirometry at Home. *Respiratory Therapy* 2018; 13:48-54
4. Stenzler A. Improving home COPD monitoring through statistical process control (SPC). *Respiratory Therapy* 2019; 14:44-47.
5. Graham BL, et al. Standardization of Spirometry 2019 Update. An Official American Thoracic Society and European Respiratory Society Technical Statement ATS/ERS Guidance. *Am J Respir Crit Care Med.* 2019; 200 (8): e70-e88

17. Schedule of Assessments

Week	-1 to-2	1 ^a	2 ^a	3 ^a	4 ^a	5 ^a	6 ^a	7 ^a	8 ^a	9 ^a	10 ^a	11 ^a	12 ^a	13
Description	Screen	Enroll/ Training /Monitor	Monitor	Monitor	Monitor	Final Call								
Subject Consent	X													
Demographics	X													
Medical History	X													
Height and Weight	X													
Vital Signs	X	X ⁱ												X
Concomitant Medications ^e	X	X ⁱ				X				X				X
Forced Spirometry		X ^c	X ^c	X ^c	X ^c	X ^c	X ^c	X ^c	X ^c	X ^c	X ^c	X ^c	X ^c	
Slow Spirometry		X ^c	X ^c	X ^c	X ^c	X ^c	X ^c	X ^c	X ^c	X ^c	X ^c	X ^c	X ^c	
Oxygen Saturation		X ^h	X ^h	X ^h	X ^h	X ^h	X ^h	X ^h	X ^h	X ^h	X ^h	X ^h	X ^h	X
CAT Quality of Life Survey	X			X					X					X
COPD Action Plan ^f		X	X	X	X	X	X	X	X	X	X	X	X	X
Medication Adherence		X	X	X	X	X	X	X	X	X	X	X	X	X
Measurement Adherence	X	X	X	X	X	X	X	X	X	X	X	X	X	X
Nurse Call		X ^b				X ^b				X ^b				X
Adverse Events ^g		X				X				X				X
Usability Survey														X

Footnotes:

a Medication and measurement reminders issue 7 days a week, medication report cards on Fridays

b Nurse will call first week of monitored months. Will call second day after enrollment/training to assure patient understanding.

c Measured with GoSpiro. Collected post-bronchodilator. Slow spirometry Sunday, Monday, Wednesday, Friday and Saturday. Forced Spirometry Tuesday and Thursday. At home measurements occur in the morning at least 15 minutes following them taking their inhaled medications.

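### The satisfaction survey is scheduled only at the final call, with no provision to ask patients who leave early, so the reported percentage is likely to be too favourable if anyone does

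*Combined protocol and SAP*

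**What the plan says.** **Collection.** Section 9.2.10 states: "At the End-of-Study phone call, the patient will be given a brief Usability Questionnaire to collect their opinions". Section 7.4 repeats this for the closing call, where staff are to "have them complete a usability questionnaire by phone". In the Section 17 schedule the row "Usability Survey" has one mark, in the week-13 final-call column. The schedule has no early-termination column.

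**Endpoint.** Section 13 (Secondary Endpoint Definitions) describes the instrument as "A satisfaction survey (investigator-developed, 15 questions, each question is graded on a scale of 1-5", with a three-month time frame. The endpoint is "defined as the percentage of participants with score of 4 or higher on individual survey domains". Under Analysis of Secondary Endpoints: "The secondary endpoints will be reported as proportion with 95% confidence interval of participants with score of 4 or higher". No analysis set, denominator or missing-data rule is attached to it. The primary outcomes do have a named set ("The primary outcomes will be reported as proportions with 95% confidence intervals, on the FAS"), but the FAS is not defined.

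**Who leaves.** Section 7.4 covers patients who, after one week, cannot provide and transmit satisfactory data for technical or training reasons: "they will be removed from study and replaced with another participant toward the total recruitment goal". Section 11 says that patients withdrawn for such reasons in the first two weeks are replaced, and it allows withdrawal at any time. For a patient who does not complete, Section 11 asks for the reason on the CRF and, after an adverse-event withdrawal, for clinical follow-up. It does not mention the questionnaire.

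**The concern.** The survey asks how easy and useful the home system is. One route out of the study, early removal for technical or training reasons, is closely tied to ease of use. A patient who struggled with the device may therefore be gone, and replaced, before the only scheduled occasion for giving an opinion.

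Whether patients accept the system is a stated purpose (Sections 4.2 and 13). Section 13 also wants the results to reveal technological deficiencies and to inform later trials. A percentage drawn only from those still present at week 13 answers a narrower question, and the patients left out are those best placed to describe the deficiencies. That the study is unpowered does not help, because selection does not depend on hypothesis testing. With about 12 patients, each omitted person can move the percentage by several points.

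**Working it through.** The plan gives no expected satisfaction rate, dropout rate or power calculation, so there is no planned figure to reproduce. The planned size of 12 is from Section 6. All counts of satisfied and unasked patients below are assumptions.

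**Formulae.** Let *x* of *n* surveyed patients score 4 or higher on a domain, and let *m* eligible, trained patients not be asked.
- Completer figure: x/n
- Worst case (no unasked patient satisfied): x/(n + m)
- Best case (all unasked patients satisfied): (x + m)/(n + m)
- If *s* of the *m* would have been satisfied, the figure for everyone is (x + s)/(n + m). The completer figure exceeds this exactly when s/m < x/n.

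Intervals are exact (Clopper-Pearson) 95%.

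**Main illustration.** Fourteen patients are trained (12 plus 2 replaced), 2 of the 12 withdraw later, and 9 of the 10 completers are satisfied. So x = 9, n = 10, m = 4.
- Completers: 9/10 = 90% (56 to 100%)
- Worst case: 9/14 = 64% (35 to 87%)
- Best case: 13/14 = 93% (66 to 100%)
- Between these, s = 1, 2, 3 give 10/14 = 71%, 11/14 = 79% and 12/14 = 86%. The completer figure is too high unless all 4 unasked patients would have been satisfied.

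**Other assumed counts**

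| Scenario | Completers | Worst case | Best case |
|---|---|---|---|
| No one leaves | 10/12 = 83.3% | 83.3% | 83.3% |
| 1 replaced | 10/12 = 83.3% | 10/13 = 76.9% | 11/13 = 84.6% |
| 4 replaced | 10/12 = 83.3% | 10/16 = 62.5% | 14/16 = 87.5% |
| 2 withdraw late | 8/10 = 80.0% | 8/12 = 66.7% | 10/12 = 83.3% |
| 2 replaced, 2 withdraw late | 8/10 = 80.0% | 8/14 = 57.1% | 12/14 = 85.7% |

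In the rows where someone leaves, the completer figure lies above the worst case by 6.4 points (83.3 − 76.9) to 22.9 points (80.0 − 57.1). It lies below the best case by 1.3 points (84.6 − 83.3) to 5.7 points (85.7 − 80.0). When most completers are satisfied there is much more room for error upward than downward. When no one leaves there is no error.

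**The case against.** A reader might infer that leavers are never asked and that satisfaction is overstated. The documents do not establish either. They are silent on a closing call for early leavers and do not forbid one; such patients presumably return equipment too. Overstatement requires that someone leaves, that leavers are less satisfied than stayers, and that they are left out of the denominator. The first two are unknown, and the third is not specified. The main illustration itself has a best case of 93%, above the completer figure of 90%.

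Other objections also have force:
- Early removal is not proof of dissatisfaction. Section 7.4 speaks of technical or training reasons, which can include a transmission or equipment fault.
- The kit is sent before eligibility is confirmed at the training appointment (Section 7.2), and inability to perform spirometry after training is an exclusion (Section 6.2). Some kit recipients are therefore screening failures. Counting each of them, or each patient withdrawn for an adverse event, as scoring below 4 would be wrong.
- Someone who used the system for a week cannot judge its value as a three-month user can.
- This is a secondary, descriptive endpoint in an unpowered 12-patient evaluation, and reasons for non-completion are recorded anyway.
- Section 11 requires a reason on the CRF, not a patient contact, so an exit questionnaire is some extra work.

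These points limit the claim and shape the remedy. They do not supply the missing provision: followed as written, the plan surveys those who reach the final call, and it has no rule to prevent or quantify the resulting selection. A reason on the CRF is not a satisfaction score.

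**Conclusion.** The point holds in conditional form. The survey has one scheduled occasion, there is no provision to ask patients who are removed, replaced or withdrawn, and no denominator is set. If anyone leaves early, the reported percentage is likely to describe those who stayed and to be too favourable.

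Direction and size are not fixed by the documents. A favourable error rests on leavers being less satisfied than stayers, which is plausible where departure follows technical or training difficulty but is not shown. The percentages in the check show what a few unasked patients could do at this sample size; they do not predict the result.

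The conclusion also assumes that the usability questionnaire of Section 9.2.10 and the 15-question satisfaction survey of Section 13 are the same instrument. The documents do not say so, but the schedule lists only one such survey. The change is worth making because the endpoint is prespecified, bears on a stated purpose, and is cheap to protect.

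**What to change.** 1. In Sections 7.4, 9.2.10, 11 and 17, provide for the same questionnaire to be attempted by phone when a removal or withdrawal is recorded, including early technical or training removals. Answering stays voluntary.
2. In Section 13, define the reporting population as all eligible patients trained on the system, including those later replaced. Report the proportion scoring 4 or higher in that population beside the completer figure.
3. Give the number not asked or not answering, with reasons, and both the worst-case and best-case bounds. Do not use the worst case alone.
4. List patients found ineligible at the training call separately, outside the denominator.
5. Reconcile the one-week passage in Section 7.4 with the two-week passage in Section 11, since together they decide who is replaced.
6. State that the usability questionnaire and the satisfaction survey are one instrument, if that is intended.

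The cost is a short extra call or questionnaire at exit, some non-response among leavers, and a reported satisfaction that may be lower.
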